**cececdde**

Today's date (Day, Month, Year):

31

**cececdde**

	Not at All	A Little	Quite a Bit	Very Much
1. Do you have any trouble doing strenuous activities, like carrying a heavy shopping bag or a suitcase?	1	2	3	4
2. Do you have any trouble taking a long walk?	1	2	3	4
3. Do you have any trouble taking a short walk outside of the house?	1	2	3	4
4. Do you need to stay in bed or a chair during the day?	1	2	3	4
5. Do you need help with eating, dressing, washing yourself or using the toilet?	1	2	3	4
During the past week:				
6. Were you limited in doing either your work or other daily activities?	1	2	3	4
7. Were you limited in pursuing your hobbies or other leisure time activities?	1	2	3	4
8. Were you short of breath?	1	2	3	4
9. Have you had pain?	1	2	3	4
10. Did you need to rest?	1	2	3	4
11. Have you had trouble sleeping?	1	2	3	4
12. Have you felt weak?	1	2	3	4
13. Have you lacked appetite?	1	2	3	4
14. Have you felt nauseated?	1	2	3	4

15. Have you vomited? 1 2 3 4

16. Have you been constipated? 1 2 3 4

### **During the past week:**

During the past week:		Not at All	A Little	Quite a Bit	Very Much
17.	Have you had diarrhea?	1	2	3	4
18.	Were you tired?	1	2	3	4
19.	Did pain interfere with your daily activities?	1	2	3	4
20.	Have you had difficulty in concentrating on things, like reading a newspaper or watching television?	1	2	3	4
21.	Did you feel tense?	1	2	3	4
22.	Did you worry?	1	2	3	4
23.	Did you feel irritable?	1	2	3	4
24.	Did you feel depressed?	1	2	3	4
25.	Have you had difficulty remembering things?	1	2	3	4
26.	Has your physical condition or medical treatment interfered with your family life?	1	2	3	4
27.	Has your physical condition or medical treatment interfered with your social activities?	1	2	3	4
28.	Has your physical condition or medical treatment caused you financial difficulties?	1	2	3	4

For the following questions please circle the number between 1 and 7 that best applies to you

29. How would you rate your overall health during the past week?

1            2            3            4            5            6            7

30. How would you rate your overall quality of life during the past week?

1            2            3            4            5            6            7

**Appendix III**  
**The European Organization for Research and Treatment of Cancer (EORTC) QLQ-BN20**

**EORTC QLQ - BN20**

Patients sometimes report that they have the following symptoms. Please indicate the extent to which you have experienced these symptoms or problems during the past week.

---

During the past week:	Not at All	A Little	Quite a Bit	Very Much
31. Did you feel uncertain about the future?	1	2	3	4
32. Did you feel you had setbacks in your condition?	1	2	3	4
33. Were you concerned about disruption of family life?	1	2	3	4
34. Did you have headaches?	1	2	3	4
35. Did your outlook on the future worsen?	1	2	3	4
36. Did you have double vision?	1	2	3	4
37. Was your vision blurred?	1	2	3	4
38. Did you have difficulty reading because of your vision?	1	2	3	4
39. Did you have seizures?	1	2	3	4
40. Did you have weakness on one side of your body?	1	2	3	4
41. Did you have trouble finding the right words to express yourself?	1	2	3	4
42. Did you have difficulty speaking?	1	2	3	4
43. Did you have trouble communicating your thoughts?	1	2	3	4
44. Did you feel drowsy during the daytime?	1	2	3	4
45. Did you have trouble with your coordination?	1	2	3	4
46. Did hair loss bother you?	1	2	3	4
47. Did itching of your skin bother you?	1	2	3	4

48. Did you have weakness of both legs?	1	2	3	4
49. Did you feel unsteady on your feet?	1	2	3	4
50. Did you have trouble controlling your bladder?	1	2	3	4

© Copyright 1994 EORTC Study Group on Quality of Life. (phase III module)

**Appendix IV**  
**Mini Mental State Exam (MMSE)**

**Folstein Mini Mental State Examination (MMSE)**

**Place Label Here**

Protocol Number \_\_\_\_\_  
 Patient ID # \_\_\_\_\_  
 Patient Initials \_\_\_\_\_  
 Date (mm/dd/yyyy) \_\_\_\_\_

\_\_\_\_/5 What is the: (year) (season) (date) (day) (month)?

\_\_\_\_/5 Where are we: (state) (county) (town) (building) (floor)?

\_\_\_\_/3 Learn: “apple, table, penny.” \_\_\_\_ # of trials

\_\_\_\_/5 Subtract serial 7’s: (100, 93, 86, 79, 72); or spell “WORLD” backwards

\_\_\_\_/3 Recall: “apple, table, penny.”

\_\_\_\_/2 Name: “pencil and watch.”

\_\_\_\_/1 Repeat: “no ifs, ands or buts.”

\_\_\_\_/3 “Take this paper in your right hand, fold it in half, and put it on the floor.”

[figure not shown]
\_\_\_\_/1 Read and obey: “Close your eyes.”

\_\_\_\_/1 Write a sentence on the back of this card.

\_\_\_\_/1 Copy the design on the back of this card

\_\_\_\_/30 Total (abnormal if <24; if <8th grade, then <21 is considered abnormal.)

# Close your eyes.

1)

2)

3)

- 4) Cochlea: Use CT bone window for contouring. Use a 6mm brush and deposit circular structure in the bone anterior to the internal auditory canal including the apical and basal turns of the cochlea. Usually on 2-3 axial slices. Alternatively, contour this volume using the free hand tool.
- 5) Eyes: In Eclipse contour the globe on the CT data set and check on any MR data set. IF discordant use CT data set.
- 6) Hippocampus: Based on RTOG guidelines (please see NRG/RTOG contouring atlas for reference), contour the subgranular zone on T1-weighted SPGR MRI. Begin contouring at the most caudal (inferior) extent of the crescentic-shaped floor of the temporal horn of the lateral ventricle and contour the hypointense grey matter located medial to the CSF hypointensity, not the white, bright white matter. The emergence of the uncal recess of the temporal horn defines the anterior boundary of the hippocampus. The medial boundary of the hippocampus becomes defined by the medial edge of the uncal recess. Postero-cranially, the medial boundary of the hippocampus is defined by the lateral edge of the quadrigeminal cistern which is the CSF containing space lateral to the pons. The hippocampal tail remains posterior to the thalamus as it curves medially toward the splenium of the corpus callosum and is still medially located relative to the lateral ventricle. Terminate hippocampal contours at the point where the T1-hypointense structure no longer borders the atrium of the lateral ventricle. At this point, the crux of the fornix emerges anteriorly and the splenium of the corpus callosum can be visualized posteriorly. If MRI is not available, a reasonable approximation can be drawn using an 8mm brush and contouring along the medial edge of the lateral ventricles from the temporal horn to posterior splenium of corpus callosum.
- 7) Hippocampus PRV: 5mm expansion of hippocampus contour

ion of brain parenchyma and  
n sparing for superficial targets.  
gittal image to define axial slice for  
ally to include midbrain (typically  
").

- 8) Hypothalamus. Follow pituitary stalk as it travels posterior to the chiasm. Posteromedial to the optic radiations are the mammillary bodies. Beginning one slice rostral to mammillary bodies, contour a cuboidal shaped structure that forms the walls of the third ventricle. It is bounded laterally by the optic radiations and posteriorly by the interpeduncular fossa and posterior commissure. Continue the contours until the hypothalamus terminates antero-rostrally at the fornix and anterior commissure.
- 9) Lacrimal gland: the lacrimal gland is located between the lateral orbital rim and the globe, beginning at the most superior and lateral aspect of the globe and extending inferiorly to the level of the lens or lateral rectus muscle.
- 10) Lens: contour on CT data set (or use auto contour in GE prior to exporting to Eclipse).
- 11) Optic chiasm. A stubby chromosome shape using a 0.3 or 0.4 mm drawing sphere. It can be located behind or anterior to the stalk. Coronal view of CT/MR is helpful as the typical MR fused for H/N brain is not sliced thin enough to pick it up accurately and it exists on multiple axial images due to its oblique course. This can be minimized when needed by simulating the patient with 17-20 degrees of chin extension (that rotates the plane of imaging into the plane of the course of the ON to the chiasm. Remember the MR should only be a guide and the CT truly defines the optic chiasm. Also do not include the carotid arteries as part of the optic chiasm contour.
- 12) Optic nerve: using a 0.3 or 0.4 mm sphere tool, contour from back of eye to chiasm. It is helpful to do chiasm first. The nerve should transit the optic canal seen on the CT data set. (see chiasm for optimizing this structure re head position for simulation). Double check the Orbital portion on the CT as this portion can move a great deal. When critical, instruct the patient to look straight ahead during simulation and MR and treatment.
- 13) Optic structures PRV: 3 mm expansion of the optic nerve and chiasm contours
- 14) Pituitary: using the FLAIR (to avoid contouring CSF) and the T1con fused data sets. Contour the gland just distal to the stalk. Do not contour the stalk itself. Check by moving to CT data set to see that structure lies in the fossa between the clinoids and the medial edge of the sphenoid bone.
- 15) Retina: use a 3 mm static sphere contour the back of the eye. To determine ant extent draw a line in the long axis of the eye, then draw a perpendicular line that bisects the posterior edge of lens. That can serve as a surrogate for the ora serrata (which can be visualized on MRI if more accuracy is needed).
- 16) Semi-circular canals: Use CT bone widow for contouring. If you include the entire bone posterior to the internal auditory canal you will include the vestibule, superior semi-circular canal, lateral/horizontal semi-circular canal, posterior semi-circular canal and vestibular aqueduct.
- 17) Skin: standard skin definition is 5mm rind on body. However, in the head, deep skin border is limited by skull. If 5mm is used, bones should be removed from skin volume. 3mm is often a closer approximation of skin in the scalp.

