#### 7.1.9 Contouring and Target Definition (please refer to diagram below)

1. Co-registration with CT scans, MRI scans, and PET scans will be used in identifying the CTV volumes
2. The doses prescribed will be based on the boolean(combined) volume of CTV defined by the PET( $T/N \geq 2.0$ ) and the MRI areas of contrast enhancement including the surgical cavity.
  - a. For patients with a combined volume  $\leq 65$  cc, over five treatment days, patients will receive 35 Gy to CTV3500\_PET, 30 Gy to CTV3000\_MR and 25 Gy(CTV2500) to boolean(combined) volume of CTV3500\_PET+CTV3000\_MR+1cm.
  - b. For patients with a combined volume  $> 65$  cc, over ten treatment days, patients will receive 40 Gy to CTV4000\_PET, 35 Gy to CTV3500\_MR and 30 Gy(CTV3000) to boolean(combined) volume of CTV4000\_PET+CTV3500\_MR+1cm.
3. The optimization target volume (OTV) is defined as a margin of 2 mm isotropic expansion of the CTV and edited clinically based on patterns of tumor spreading and anatomic boundaries such as skulls and nasal cavity.
4. All normal structures will be contoured on the standard of each institution.

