### Prescription Deviations and Goals

	Goal	Min deviation (2)	Major deviation (1)
CTV	D95% = 95%	D95% = 85% - 120%	<85% or >120%

- Prescription Dose: we recommend that in the worst-case scenario the CTV D95% is at least 95% of the prescription dose and the CTV D5% is at most 120% of the prescription dose.
- Minor deviation: CTV D95%: 85-95% of the prescription dose, CTV D5%: 110-120% of the prescription dose in the worst-case scenario.
- Major deviation: CTV 95% : <85% of the prescription dose, CTV D5%: >120% of the prescription dose in the worst-case scenario.
- Volume: The CTV must be specified on any plans with dose –volume histograms for these and all critical organs
- Critical structures in Table 7.1 with the dose volume indices up to 110% of the limit will be considered a minor deviation. Critical structures in Table 7.1 with the dose volume indices more than 120% of the limit will be considered a major deviation.

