#### 7.1.13 Critical Structures

Table 7.1 Dose volume constraints for critical structures in the nominal scenario. Minor deviation (110% of the limit) is allowed in the worst-case scenario

FIVE FRACTION	Volume	Volume Max Gy[RBE]	Max Point Dose Gy[RBE]
Optic Pathway	<0.2 cc	23 Gy[RBE]	25 Gy[RBE]
Brainstem	<0.5 cc	23 Gy[RBE]	31 Gy[RBE]
Skin	<10 cc	36.5 Gy[RBE]	38 Gy[RBE]

TEN FRACTION	Volume	Volume Max	Max Point Dose
Optic Pathway	<0.5cc	32 Gy[RBE]	37.5 Gy[RBE]
Brainstem	<0.5 cc	33 Gy[RBE]	40 Gy[RBE]
Skin	<10 cc	43.2 Gy[RBE]	45.6 Gy[RBE]

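### Appendix V gives a 0.3 or 0.4 mm drawing tool for the optic nerve and chiasm; if that sets the contour width, the Table 7.1 optic volume limits cannot act

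*Combined protocol and SAP*

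**What the plan says.** Appendix V (Contouring Guidelines) gives the same tool size for two optic structures. Item 12 says "Optic nerve: using a 0.3 or 0.4 mm sphere tool, contour from back of eye to chiasm". Item 11 describes the chiasm as "A stubby chromosome shape using a 0.3 or 0.4 mm drawing sphere". Item 13 then defines a planning volume: "Optic structures PRV: 3 mm expansion of the optic nerve and chiasm contours". For the retina, item 15 says "use a 3 mm static sphere contour the back of the eye". The cochlea (item 4) has a 6 mm brush, and the hippocampus (item 6) has an 8 mm brush as a fallback when there is no MRI.

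Table 7.1 in section 7.1.13 limits the optic pathway by a volume at a stated dose and, separately, by a maximum point dose. The five-fraction row is "Optic Pathway <0.2 cc 23 Gy[RBE] 25 Gy[RBE]" and the ten-fraction row is "Optic Pathway <0.5cc 32 Gy[RBE] 37.5 Gy[RBE]". The text on prescription deviations grades plans on these indices: up to 110% of the limit is minor, and "Critical structures in Table 7.1 with the dose volume indices more than 120% of the limit will be considered a major deviation". Section 7.1.14 turns the grades into an overall plan rating.

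Section 7.1.9, item 4, says "All normal structures will be contoured on the standard of each institution".

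**The concern.** A limit of the form less than 0.2 cc above a given dose can only be broken by a structure larger than 0.2 cc. A structure drawn as a line 0.3 or 0.4 mm wide is far smaller than that over any plausible optic length. The volume criterion would then pass whatever the dose, and the plan rating in 7.1.14 would rest on the point dose alone for this organ.

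The tool size stands in an operating instruction for a critical structure, appears twice, and does not fit the other tools in the appendix. The protocol also does not say whether Appendix V or each institution's standard governs, or which contour Table 7.1 means by Optic Pathway.

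**Working it through.** The documents state no optic volume, so there is no plan figure to reproduce. The check is geometric.

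**Inputs from the protocol.** Tool width d = 0.3 or 0.4 mm (Appendix V, items 11 and 12). Volume limits 0.2 cc = 200 mm³ and 0.5 cc = 500 mm³ (Table 7.1). Volume-limit doses 23 and 32 Gy[RBE]; point-dose limits 25 and 37.5 Gy[RBE] (Table 7.1). PRV margin 3 mm (Appendix V, item 13).

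**Assumption.** Total centre-line length L of both nerves and the chiasm is 80 to 200 mm. This is not in the documents.

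**Step 1: volume of a single-pass contour.** Area = πd²/4, which is 0.0707 mm² at 0.3 mm and 0.1257 mm² at 0.4 mm. Volume = area × L.

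| d | L = 80 mm | L = 200 mm |
|---|---|---|
| 0.3 mm | 0.0057 cc | 0.0141 cc |
| 0.4 mm | 0.0101 cc | 0.0251 cc |

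The largest value, 0.0251 cc, is about one eighth of 0.2 cc and one twentieth of 0.5 cc.

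**Step 2: length needed to reach the limit.** Limit ÷ area.

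| d | 0.2 cc | 0.5 cc |
|---|---|---|
| 0.3 mm | 2,829 mm | 7,074 mm |
| 0.4 mm | 1,592 mm | 3,979 mm |

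The result therefore does not depend on where L falls in the assumed range.

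**Step 3: other readings of the instruction.**
- Tool size as a radius (d = 0.6 or 0.8 mm): 0.023 to 0.101 cc, still below both limits.
- Tool used to fill in a wider outline: 0.2 cc is reached at a mean width √(4 × 200/(πL)) of 1.78 mm (L = 80 mm) to 1.13 mm (L = 200 mm). That is about 20 to 8 non-overlapping passes at 0.4 mm.
- Limits applied to the 3 mm PRV (d = 0.4 + 6 = 6.4 mm): 2.57 to 6.43 cc, above both limits.
- For scale only, a width of 3 or 4 mm gives 0.57 to 1.41 cc or 1.01 to 2.51 cc, so both limits could act.

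**Step 4: how much dose excess the point-dose limit leaves unseen.** If the point-dose limit is met, no part of the contour exceeds it. The largest dose relative to the volume-limit dose is 25/23 = 1.087 (five fractions) and 37.5/32 = 1.172 (ten fractions). Reading the deviation percentages as percentages of dose, 109% lies within the minor band and 117% lies below the major threshold.

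**The case against.** A reader might infer that the optic volume limits can never be exceeded in this trial, or that overdosed plans have been passed. The documents do not support either inference, for four reasons.

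- **A drawing tool is not a structure width.** Item 11 asks for a shape followed over several axial images, leaves out the carotid arteries, and makes the CT decisive for the chiasm. That describes outlining visible anatomy, which would give a larger volume. This stands. It limits the problem to planners who take the tool size as the width.
- **The limits might apply to the PRV.** Item 13 defines one, and Table 7.1 does not define Optic Pathway. On the PRV the limits could act. This also stands, although nothing in the text ties Table 7.1 to the PRV.
- **Institutional standard may govern.** Section 7.1.9 item 4 says so for normal structures, and section 7 does not cite Appendix V in the text available. The opening items of the appendix are incomplete in that text, so a statement of its status may be missing, and the appendix may itself be the institutional standard. It is therefore not shown that the two sites contour differently.
- **The point-dose limit caps the hidden excess.** Step 4 holds for a plan that meets that limit, with three qualifications. A very thin contour may miss the true maximum. A plan over the point-dose limit falls outside the bound, although it would be flagged on that limit. The bound is on dose; if the deviation percentages are read as volume, it does not limit the volume affected.

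The protocol also keeps LET or biologic-dose review for the chiasm (7.1.11) and investigator review of every plan (7.1.14). No analysis in section 16 expressly uses the plan rating.

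What remains is a tool size that leaves the volume limits without effect if followed literally, and no statement of which structure or rule applies.

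**Conclusion.** The concern holds in a conditional form and is minor. If the stated tool width is the contour width in a single pass, the whole optic contour is about 0.006 to 0.025 cc, and both Table 7.1 volume limits are met at any dose. This rests on the single-pass reading, on applying the limits to the nerve and chiasm contour rather than the PRV, on planners following Appendix V, and on the assumed 80 to 200 mm length, to which the result is insensitive. For a plan that meets the point-dose limit, the unseen dose excess is at most about 9% (five fractions) or 17% (ten fractions), if the contour captures the maximum. A slip between millimetres and centimetres would explain the figure, but the documents do not confirm it, and they do not show that any plan was contoured this way.

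**What to change.** 1. Radiation oncology and physics should check and correct the tool size or its unit in Appendix V items 11 and 12, and reconcile it with Table 7.1.
2. State in Table 7.1 whether Optic Pathway means the nerve and chiasm contour or the PRV of item 13.
3. State in 7.1.9 item 4 whether Appendix V or institutional standard governs normal structures.
4. For plans already rated, compare the stored optic contours with the visible anatomy. Re-contour and then re-rate only those drawn at the sub-millimetre width. Re-rating the same thin contour would change nothing, because its volume criterion would still pass.

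No dose limit or particular tool size is proposed here. The cost is a short wording change in three places and a review of contours stored in the planning system, with re-contouring only if that review finds any such plan.

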## Appendix VI

PLACE LABEL HERE		MAYO CLINIC CANCER CENTER		
Protocol Number: MC1774	Patient Initials: _____		Imaging Form	
Patient ID: _____	L	F	M	
Institution Number: _____	ALL ITEMS MUST BE COMPLETED			
Institution: _____	Are data amended? (check one)  Yes  No (If data amended, please circle in red when using paper forms)			

Current Cycle Number: \_\_\_\_\_

#### IMAGING DETAILS

##### MR

Was conventional MR imaging completed? (check one)

1  Yes. If Yes: Date of conventional MR imaging: (mm/dd/yyyy) \_\_\_\_\_ / \_\_\_\_\_ / \_\_\_\_\_

2  No. If No, Primary Reason conventional MR imaging not completed:

99  Other (not per protocol), specify \_\_\_\_\_

Was perfusion MR imaging completed? (check one)

1  Yes. If Yes, date perfusion MR imaging completed? (mm/dd/yyyy) \_\_\_\_\_ / \_\_\_\_\_ / \_\_\_\_\_

2  No. If No, Primary Reason perfusion MR imaging not completed:

99  Other (not per protocol), specify \_\_\_\_\_

Was diffusion MR imaging completed? (check one)

1  Yes. If Yes, date diffusion MR imaging completed? (mm/dd/yyyy) \_\_\_\_\_ / \_\_\_\_\_ / \_\_\_\_\_

2  No. If No, Primary Reason diffusion MR imaging not completed:

99  Other (not per protocol), specify \_\_\_\_\_

##### PET

Weight (kg): \_\_\_\_\_ (used for this cycle, round to the nearest tenth)

Is this patient of childbearing potential? (check one)      1  Yes      2  No

If Yes: Negative pregnancy test date (≤ 48 hours prior to injection of study drug): (mm/dd/yyyy) \_\_\_\_\_ / \_\_\_\_\_ / \_\_\_\_\_

Pregnancy test date time: \_\_\_\_\_; \_\_\_\_\_ (military time)

Was FDOPA-PET imaging completed? (check one)

1  Yes. If Yes: Date of FDOPA-PET imaging: (mm/dd/yyyy) \_\_\_\_\_ / \_\_\_\_\_ / \_\_\_\_\_ Time

of Injection: \_\_\_\_\_ : \_\_\_\_\_ [Range: 0000 (midnight) to 2359 (11:59 pm)]

FDOPA Dose amount: \_\_\_\_\_ mCi

Time of FDOPA-PET imaging: \_\_\_\_\_ : \_\_\_\_\_ [Range: 0000 (midnight) to 2359 (11:59 pm)]

Duration of scan (minutes): \_\_\_\_\_

2  No. If No, Primary Reason FDOPA-PET imaging not completed: (check one)

49  Allergic reaction

223  Vasovagal reaction

218  Bruising

229  Rash/maculo-papular

99  Other (not per protocol), specify \_\_\_\_\_
